### 23.0 Appendix E – Matching Algorithm

To address inherent uncertainties in the comparison of polyp localizations and sizes, a polyp-matching algorithm will be used to determine the agreement between CCE/CTC and OC. The first step of this procedure is to identify all polyps  $\geq 6$ mm detected by any method (OC, CCE, or CTC). The polyp with the largest estimated diameter of either OC or CCE/CTC will be referred to as the ‘reference’ polyp. The colon segment location (cecum, ascending, transverse, descending/sigmoid, or rectum) of the reference polyp will be determined and recorded. The largest polyp identified using the other method within the same or an immediately adjacent segment location of the “reference” polyp will be used to determine agreement based on a size matching algorithm. If there were two polyps of equal size that were “the largest” and located in different segments of the colon, then the location and size matching algorithm will be repeated for each of these reference polyps to determine agreement of CCE/CTC with OC.

For a given polyp to be considered a match between CCE/CTC and OC, it has to be assessed within 50% (plus or minus) of the size of the largest estimate of the two studies (CCE and OC or CTC and OC) and must appear within the same or immediately adjacent colon segments.

For example, if CCE detected a 10 mm polyp, the  $\pm 50\%$  range would be 5-15 mm. If colonoscopy detected a 6 mm polyp ( $\pm 50\%$  range = 3-9mm) in the same or immediately adjacent segment, the 2 polyps would be considered a match (CCE true positive) because the two ranges overlap.

The “reference” polyp size will then be used to assign the polyp to the following groups:  $\geq 6$  mm, and/or  $\geq 10$  mm in size. For each subject, the CCE/CTC evaluation will be classified into one of four categories of agreement relative to OC, as shown in Table 3.

Table 3. Polyp Matching Accuracy Assessment

Findings of CCE or CTC	Findings of blinded or unblinded colonoscopy	
	Positive	Negative

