Positive	
True positive (A)
 
Polyps <math>\geq 6</math>mm: Polyp matching exists and “reference” polyp size is <math>\geq 6</math> mm
 
Polyps <math>\geq 10</math>mm: Polyp matching exists and “reference” polyp size is <math>\geq 10</math> mm
	
False positive (B)
 
Polyps <math>\geq 6</math>mm: No polyp matching and CCE/CTC is <math>\geq 6</math> mm
 
Polyps <math>\geq 10</math>mm: No polyp matching and CCE/CTC polyp is <math>\geq 10</math> mm

Negative	
False negative (C)
 
Polyps <math>\geq 6</math>mm: No polyp matching and OC polyp is <math>\geq 6</math> mm
 
Polyps <math>\geq 10</math>mm: No polyp matching and OC polyp is <math>\geq 10</math> mm
	
True negative (D)
 
Polyps <math>\geq 6</math>mm: All reported polyps are <math>< 6</math> mm
 
Polyps <math>\geq 10</math>mm: All reported polyps are <math>< 6</math> mm, or Polyp matching exists and “reference” polyp size is <math>< 10</math> mm

The accuracy measures will be calculated based on the matched results, including sensitivity, specificity, positive predictive value (PPV) and negative predictive value (NPV).

Additionally, sensitivity analyses including varying matching sizes and using OC as the reference will be performed to assess the robustness of the results.

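### Appendix E gives two different size-matching tests, and Table 3 as printed does not place every subject in exactly one cell

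*Combined protocol and SAP*

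**What the plan says.** Appendix E (section 23.0) sets out the matching in these steps.

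- **Candidates.** "The first step of this procedure is to identify all polyps" of 6 mm or more found by any method. The largest is the reference polyp. Its partner is "The largest polyp identified using the other method within the same or an immediately adjacent segment location".
- **Size rule.** For a match, "it has to be assessed within 50% (plus or minus) of the size of the largest estimate of the two studies", and the two polyps must lie in the same or adjoining segments.
- **Worked example.** CCE 10 mm (range 5–15 mm) and OC 6 mm (range 3–9 mm) "would be considered a match (CCE true positive) because the two ranges overlap".
- **Ties.** If two equally large polyps lie in different segments, "then the location and size matching algorithm will be repeated for each of these reference polyps to determine agreement of CCE/CTC with OC".
- **Classification.** For each subject, "the CCE/CTC evaluation will be classified into one of four categories of agreement relative to OC". In Table 3, cell A (true positive) needs a match with the reference at or above the threshold. Cell B (false positive) reads "No polyp matching and CCE/CTC is" at or above the threshold. Cell C (false negative) reads "No polyp matching and OC polyp is" at or above the threshold. Cell D (true negative) needs every reported polyp to be under 6 mm or, on the 10 mm line only, a match with a reference under 10 mm.

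The four accuracy measures come from this table. At 6 mm they are the secondary endpoints (section 8.3); section 9.3 adds 10 mm. Section 8.11.1 points to the matching algorithm straight after saying that yield is calculated in relation to OC.

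**The concern.** The size rule puts one range around the larger reading. The example puts a range around each polyp and asks whether the ranges meet. These are different tests, and the example's own pair passes both, so it does not show which is meant.

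Table 3 has a separate problem. Cells B and C each require no match plus a size on one method, and neither excludes the other. At 10 mm, some unmatched subjects satisfy no cell. Two programmers who follow the text faithfully could therefore report different sensitivity, specificity, PPV and NPV from the same data. The choice of size test also decides who is a true positive, so it could move diagnostic yield as well if yield is the true-positive share. Sections 8.2 and 8.11.1 imply that but do not state it.

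**Working it through.** **1. The plan's example.** 10 × 0.5 to 10 × 1.5 = 5–15 mm; 6 × 0.5 to 6 × 1.5 = 3–9 mm. Both ranges reproduce.

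**2. The two tests.** Let L be the larger and s the smaller size.

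- Rule: s ≥ 0.5L, so s/L ≥ 1/2. The upper limit 1.5L never binds.
- Overlap: 1.5s ≥ 0.5L, so s/L ≥ 1/3 (strictly greater if ranges that only touch do not count).

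| Pair, same segment | s/L | Rule | Overlap |
|---|---|---|---|
| 10 and 6 mm | 0.60 | match | match |
| 14 and 6 mm | 0.43 | none (6 < 7) | match (7–21 and 3–9) |
| 18 and 7 mm | 0.39 | none (7 < 9) | match (9–27 and 3.5–10.5) |

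Overlap is always the looser test. If both polyps must be 6 mm or more, disagreement needs 6 < L/2, so L > 12 mm; the first whole-millimetre pair is 13 and 6. If the partner may be smaller, disagreement starts at 7 and 3 mm (6 and 2 mm if touching ranges count).

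**3. Cells B and C.** Take CCE 8 mm in the rectum and OC 7 mm in the cecum, with the rectal polyp still not confirmed after the unblinded OC. The segments are not adjacent, so there is no match. At 6 mm, B holds (CCE 8 ≥ 6) and C holds (OC 7 ≥ 6). Read for the whole subject, the row and column headings (positive, positive) point to A, whose text requires a match.

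**4. Gap at 10 mm.** Take CCE 7 mm and no OC polyp. A fails (no match), B fails (7 < 10), C fails (no OC polyp), and D fails (7 is not under 6, and there is no match). The same holds for every unmatched subject whose largest polyp is at least 6 but under 10 mm. There is no such gap at 6 mm.

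**5. Worth of one subject in the B/C overlap, CCE arm.** Inputs: 160 per arm less 10% attrition (section 9.1) = 144; OC yield 28%, CCE sensitivity 81% and specificity 93% at 6 mm (section 6.2, Table 1, the 695-subject screening study).

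- OC-positive 0.28 × 144 = 40.3: true positives 0.81 × 40.3 = 32.7, false negatives 7.7 (rounded).
- OC-negative 103.7: true negatives 0.93 × 103.7 = 96.4, false positives 7.3.

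| Measure | Counted in C | Counted in B |
|---|---|---|
| Sensitivity | 81.0% | 32.7/39.3 = 83.1% |
| Specificity | 93.0% | 96.4/104.7 = 92.1% |
| PPV | 81.8% | 32.7/40.9 = 79.8% |
| NPV | 92.6% | 96.4/103.1 = 93.5% |

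Cell A is unchanged, so yield is unchanged.

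**6. Worth of one subject under the size test.** If yield is cell A over the arm, one subject is 1/144 = 0.69 points.

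**7. Size of the 10 mm gap, same study** (10 mm figures: 11%, 80%, 97%). Unmatched at 6 mm but not at 10 mm: (0.28 × 0.19 − 0.11 × 0.20) + (0.72 × 0.07 − 0.89 × 0.03) = 0.0312 + 0.0237 = 5.5%, about 8 of 144. Leaving them out rather than counting them in D moves specificity from 124.3/128.2 = 97.0% to 116.4/120.3 = 96.8%, and NPV from 97.5% to 97.4%.

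**The case against.** The mandatory sentence is the half rule. The overlap clause is only a reason inside an example whose result agrees with that rule, so most readers would take the rule as controlling. That is fair, and it is why the rule should be kept. Still, the only worked illustration teaches the looser test.

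Several safeguards come before or alongside Table 3. A result that is not congruent with the blinded OC triggers an unblinded OC (sections 8.0 and 8.11.1, Appendix C3), and Table 3 uses the findings of either examination. A rectal polyp confirmed at a matching size would move the subject in the example above to A. The Clinical Events Committee (CEC) adjudicates OC size where sizes disagree. Sensitivity analyses with other matching sizes, and with OC as the reference, are planned. These reduce the number of affected subjects, but none says which size test is primary or where a subject who remains unmatched belongs.

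Cells B and C could also be separated by the source of the reference polyp: B if it came from CCE/CTC, C if from OC. That is workable, but the text does not say it, and equal largest readings on the two methods would still need a rule.

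A reader might also take the unstated 6 mm floor for the partner polyp and the unstated scoring of disagreeing ties as further contradictions. They are missing detail. The first step can be read as restricting all candidates to 6 mm or more.

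**Conclusion.** Appendix E is wrong as written on two counts, with modest weight. Its rule and its example's reason are different tests (about 1/2 and 1/3). Table 3 does not deliver one cell per subject: B and C overlap at both thresholds, and unmatched 6–9 mm subjects have no cell at 10 mm. The overlap changes the four accuracy measures by roughly 1 to 2 points per subject, but not yield. The gap touches only the 10 mm measures, by 0.1 to 0.2 points.

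These sizes assume 144 evaluable subjects in the arm and borrow one earlier study's accuracy, whose matching rule the plan does not give. They cover the CCE arm only. The documents give no joint distribution of size and location, so the number of affected subjects cannot be derived.

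A reader might infer that one reclassified subject could decide the primary non-inferiority result. The documents do not support that. The link from cell A to yield is implied rather than stated, no prior is given, and the matching rule acts on both arms. With assumed flat Beta(1,1) priors, one can pick counts at which a single CCE subject crosses the 96% final bar (25 to 26 against CTC 22, of 144: 0.948 to 0.961). Adding one subject in each arm gives 0.945, and at about the planned rates (36 against 22) the probability is 0.999.

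**What to change.** In Appendix E and Table 3:

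1. Keep the size rule as the primary test: smaller size at least 50% of the larger, same or adjoining segment. Delete the overlap reason from the example. Overlap may be one of the planned matching-size sensitivity analyses.
2. State that cells are assigned after the unblinded OC, in a fixed order at each threshold. For example: A if a reference polyp at or above the threshold is matched; otherwise C if OC reports a polyp at or above it; otherwise B if CCE/CTC does; otherwise D. This makes the cells exclusive and exhaustive, keeps every OC-positive subject in the sensitivity denominator, and closes the 10 mm gap.
3. Report the reverse B/C order as a sensitivity analysis. The downside of C before B is that it lowers sensitivity and NPV and raises specificity and PPV compared with the reverse.
4. In the same edit, clarify whether a partner polyp under 6 mm can count as a match, how a subject is scored when tied reference polyps disagree, and whether yield is the cell A share. Correct the section 8.11.1 pointer from Appendix D to Appendix E.

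Fix these choices before arm-level results are seen, since investigators know the assigned arm and interim analyses come every 80 subjects. The cost is a few sentences and one cross-reference. No new data are needed: OC size is documented for every polyp (Appendix C3), and Appendix A4 sets no minimum size for recording CCE polyps.
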